**Is there a potential for subjects to benefit directly from participation in the study?**

Yes

q23302

**Describe the potential benefits to be gained by the individual SUBJECT. Please note that payment for participation is not considered a benefit.**

As a result of this study, we anticipate that the participants may take their medications better, contributing to better adherence.

q23303

**State the potential benefits or information which may accrue to SCIENCE or SOCIETY in general as a result of this work.**

The immediate impact of this study will be data to inform the design of a future, fully powered, efficacy trial. If findings are as expected, we will proceed to an R01 application. If findings are not as expected (e.g., negative), we will work to improve the SystemCHANGE™ intervention or move to a different intervention in future trials. The long-term impact of this line of research will be additional empirical evidence for novel medication adherence interventions in this population to inform future evidence-based guidelines, position statements, and practice recommendations.

---

#### **F-Data Safety Monitoring**

q23304

**Describe the provisions for monitoring the data to ensure the safety of subjects.**

Complete plan in attachment.

---

#### **H-Informed Consent**

q901

**Will all or some subjects consent to participate in the research?**

All subjects (or their legally authorized representative) will consent to participate in the research

q909

**For those subjects who will consent to participate, explain how subjects (or subjects' legally authorized representative) will be presented with the information needed to decide to participate, including all elements of informed consent.**

Recruitment sites will generate lists of potentially eligible patients using electronic health record data to ensure a match with eligibility requirements with regard to prescribed RAAS inhibitors, diagnosis and stage of CKD and proteinuria. The study staff will randomly select each potential participant from the list using a biostatistician produced list of random numbers, and mail letters to identified patients describing the study and opt-out procedures to avoid being contacted by the study staff. The study staff will contact patients by phone to discuss possible study participation and, if interested, verify study eligibility including administering the cognitive screener. If interested and eligible, the study staff will mail consent documents with instructions for returning them by mail/email. After receiving the signed consent, the participant will move into the screening phase. Staff will record reasons for those not eligible or not interested in the study.

q903

**Describe any informed consent tools which will be used to present information to potential subjects (i.e. consent documents, videos, brochure, drug/device information, etc) and how they will be used.**

Informed consent documents will be mailed to the participants and asked to be mailed back after the initial screening of inclusion/ exclusion criteria and an informal agreement to participate. The initial screening via telephone will provide details of the study including any risks or benefits as well as answer any questions pertaining to the study. The informed consent documents also provide an opt-out at any time by contacting the primary investigator ([name]) at [name]. In clinic recruitment participants will complete the informed consent at time of contact.

q925

**Describe the timing of the informed consent process, including how you will ensure potential subjects have sufficient opportunity to discuss and consider participation before agreeing to participate in the research.**

Because the initial screening takes place via telephone and informed consent is to be obtained via mail for participation, there is a period of days between the telephone call, returned signed consents, and an initial visit via phone or virtually. This ensures that participation is voluntary, there is sufficient time to consider participation, and multiple opportunities to discuss involvement further, as well as change their decision.

q30127a

**Will you include all required elements of consent in your consent process?**

Yes

q921

**Indicate in what language(s) the consent conversation will be conducted.**

English

q926

**Explain how you will ensure potential subjects understand the information you have presented to them before they agree to participate in the study.**

We will leave time for questions with potential participants. We will utilize the "teach back" method to allow participants a chance to explain the information given to them about the study in their own terms.

q929

**Briefly describe any training provided to investigators who are obtaining informed consent.**

Staff will be trained rigorously in study procedures. Prior to the start of the study, staff will engage in role-play and simulation. All staff working on this study have completed CITI training.

q931

**Does the research include any minimal risk procedures to which subjects will not consent?**

No

q23678a

**For those subjects who will consent to participate, choose whether the consent process will be documented by a written signature from subjects.**

All consented subjects will provide a written signature as documentation of consent.

q30129a

**Will subjects participate in any study activity prior to physically signing a consent document?**

No

q940a

**Explain the process for obtaining a written signature from subjects.**

After names are given by the provider, then randomly selected to be contacted for potential participation in this study, the participants are contacted via telephone for initial screening of inclusion/ exclusion criteria. The consent form is mailed to participants and the signed consent form will be mailed back with a provided self-addressed, stamped envelope before participation in this study. Those recruited in the clinic setting will be informed of the study procedures and two informed consents, one to sign and one to maintain for their records.

---

---

**K-HIPAA**

q23253

**Are you part of a covered entity (health care provider that transmits health information electronically) or are you receiving information from a covered entity as part of your research?**

Yes

q23254

**Will protected health information be utilized, accessed, collected, or generated as part of the study?**

Yes

q30347a

**Select the electronic systems to be used for the collection and/or storage of protected health information (ePHI). Choose all that apply.**

REDCap

---

q23257

**Will you be accessing or collecting protected health information for RECRUITMENT purposes?**

Yes

q23258

**Choose all that apply to the recruitment plans.**

Health information provided by clinicians not part of the study team

q23271

**Will the clinician direct the potential subject to contact the study team?**

Yes

q23277

**HIPAA applies to your study, and requires that you obtain authorization for PARTICIPATION in research, or that you request a waiver. Check all that apply.**

I will obtain written, signed authorization from subjects prior to their participation

q23278

**Will you be collecting information from subjects' medical records?**

Yes, I have uploaded an Authorization template to the Attachments section.

---

## Attachments

---

Attachment Type

Data Collection Instrument

Attachment

[EMM Discrepancy Log.docx](#)

Name

EMM Discrepancy Log

Comments

Attachment Type

Data Collection Instrument

Attachment

[13 Health Care Use Form Revision 3.docx](#)

Name

Health Care Use, Medical Appointments Form

Comments

Attachment Type

Data Collection Instrument

Attachment

[9B Intervention Steps 1 and 2 Important People Etc. Forms Revision 2.docx](#)

Name

Important People Form, Life Routine Form, Solutions Form

Comments

Attachment Type

Data Collection Instrument

Attachment

[9C Intervention Steps 3 and 4 Questions.docx](#)

Name

Questions for SystemCHANGE

Comments

Attachment Type

Data Collection Instrument

Attachment

[PAM-13 .docx](#)

Name

PAM-13

Comments

Attachment Type

Data Collection Instrument

Attachment

[R01\\_Ellis\\_Medical History.docx](#)

Name

Medical Record Form

Comments

Attachment Type

Data Collection Instrument

Attachment

[Social Support Appraisal.docx](#)

Name

Social Support Appraisal

Comments

Attachment Type

Data Collection Instrument

Attachment

[Acceptability Scales to add to appendix [name].docx](#)

Name

Acceptability Scale

Comments

Attachment Type

Data Collection Instrument

Attachment

[R21\\_Acceptability\\_Scale \(1\).docx](#)

Name

Accept

Comments

Attachment Type

Data Collection Instrument

Attachment

[EllisAppendix-3.pdf](#)

Name

Mental Status Screen, Systems Thinking, Demographic Form, Electronic Medication Monitoring Discrepancy Log, Medical History data collection form questionnaire, Perceived Health Status

Comments

Attachment Type

HIPAA Authorization Form

Attachment

[MAGICIAN HIPPA.docx](#)

Name

HIPPA

Comments

Attachment Type

Protocol

Attachment

[R21\\_MAGICIAN\\_Intervention Figure2 Updated.xlsx](#)

Name

Figure 2 restart

Comments

Attachment Type

Recruitment Materials

Attachment

[Recruitment Script 10.31.2023.docx](#)

Name

Script for phone calls

Comments

Attachment Type

Recruitment Materials

Attachment

[Brochure MAGICIAN Final.pptx](#)

Name

Brochure for participants

Comments

Attachment Type

Recruitment Materials

Attachment

[Recruitment Letter Final- restart.docx](#)

Name

Recruitment letter

Comments

Attachment Type

Recruitment Materials

Attachment

[Amended\\_MAGICIAN\\_DSM.docx](#)

Name

Comments

Attachment Type

Recruitment Materials

Attachment

[MAGICIAN\\_STUDY-physician flyer 7.11.22.png](#)

Name

Comments

Attachment Type

Recruitment Materials

Attachment

[Magician Patient Pamphlet copy.png](#)

Name

Comments

Attachment Type

Recruitment Materials

Attachment

[KIDNEY DESIGN.pdf](#)

Name

Comments

Attachment Type

Other

Attachment

[MAGICIAN IFC amended letter.docx](#)

Name

Comments

Attachment Type

Recruitment Materials

Attachment

[MAGICIAN Study Image Flow \\_RJE.docx](#)

Name

Imagery for recruiting to streamline conversations with potential participants.

Comments

Attachment Type

Recruitment Materials

Attachment

[Clinic RA Screening Tool.docx](#)

Name

Screening tool to facilitate conversations between RA's and Physicians

Comments

Attachment Type

Informed Consent Statement

Attachment

[Final \\_MAGICIAN\\_IFC\\_10.31.2023.docx](#)

Name

Comments

# Administrative Details Form

## Protocol Details

9031

Protocol Type  
Expedited

Billing Account #

Study Status

---

## Protocol Determinations

9003

Protocol Level of Risk.

Minimal risk

9020

Is renewal required for this research?

No

9004

Check all determinations that need to be made.

Certificate of Confidentiality

9025

Certificate of Confidentiality.

The research is subject to the NIH Policy for Issuing Certificates of Confidentiality and therefore has been issued a Certificate.

9028

Other Determinations.

---

---

### **Statistical Design and Power.**

**A.1. Statistical Design.** This two-arm randomized single masked experimental design pilot study compares SystemCHANGE™ with attention control patient education using repeated measures in adults with CKD and poor adherence to prescribed RAAS inhibitor medication. Randomization will be stratified by *moderate* (.70 - .84) and *low* (<.70) *medication adherence*.

**A.2. Sample Size Justification and Power Analysis.** Sample size is based on considerations for designing pilot studies and based on this study's aims. Hertzog suggests 30 participants per group is sufficient for estimating preliminary efficacy. Based on these practical considerations and anticipated attrition based on our prior studies, we will enroll 66 individuals, to retain 60 with CKD stage 1-4 and poor adherence. The resulting 30 participants per group will be sufficient for estimating preliminary efficacy. Statistical analyses will be conducted to determine acceptability, outcome expectancy and credibility (Aim 1) and to calculate preliminary effect size estimates (Aim 2) that may be used in combination with other evidence to justify a future randomized trial; however, efficacy estimates themselves will not solely be used to determine the sample size for the larger study (Leon AC, Davis LL, Kraemer HC. The Role and Interpretation of Pilot Studies in Clinical Research. *J Psychiatr Res* 2011 May; 45(5): 626-629; doi:10.1016/j.jpsychires.2010.10.008).

**A.3. Analytic Plan.** We will conduct rudimentary analyses to ensure that data have been properly collected and to identify outliers or errors. Data manipulation and analysis will be conducted in SAS Version 9.4 (SAS Institute Inc., Cary, N.C.) and all syntax documented to ensure reproducibility. We will calculate the proportion eligible that enroll and complete the intervention. Aim 1: We will tabulate responses to acceptability, outcome expectancy and credibility items. Aim 2: Effect sizes will be estimated by fitting ANCOVA models with treatment group as the explanatory variable and outcomes: 1) adherence and 2) personal systems behavior. Effects sizes will be estimated with  $\omega^2$ . Analyses will be intent-to-treat. Supplementary analyses will investigate how the adjustment for levels of the covariate (e.g. male and female for sex) impacts effect size estimates by adding interaction terms to models and estimating effect sizes separately for the different levels. **Missing Data:** We will compare baseline variables between subjects who drop out of the study to those who do not using two-sample *t* tests, chi-square tests or non-parametric equivalents as appropriate. If we find that missing data appear to be not missing at random, this information will be used in designing the larger trial. Due to the relatively small sample size, we will not attempt to model the missing data mechanism in this pilot study. **Sex as a biological variable:** As noted above, we will estimate effect sizes by sex for all outcomes. Additionally, for Aim 1, qualitative interviews will be recorded, transcribed verbatim, and entered into the NVivo 12 (QSR Int.) qualitative software. We will use standard content analysis procedures to code data into meaningful categories regarding acceptability. The resulting qualitative data will be combined with quantitative data in side-by-side summary tables to derive integrative summary statements to draw conclusions about participant acceptability.

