## **Select the appropriate status of the study.**

Closed to Enrollment – Research interventions continue

4004

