## **Why are these changes being made (i.e. what is the rationale for these changes)?**

To increase understanding of how SystemCHANGE can increase medication adherence in those who have chronic kidney disease. Previous enrollment numbers are not significant for complete data analysis. Even though not a true crossover design, the increased enrollment in the SYstemCHANGE intervention will lead to better discoveries to yield R01 funding.

4006

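### The SAP still calls 30 per group sufficient, although the current amendment reports enrolment closed at numbers it treats as inadequate, and moving controls into SystemCHANGE cannot restore 30 versus 30

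*SAP*

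**What the plan says.** SAP A.2 rests the sample size on pilot-study guidance: "Sample size is based on considerations for designing pilot studies". It then sets the target, "we will enroll 66 individuals, to retain 60 with CKD stage 1-4 and poor adherence", with the allowance for loss explained only as "Based on these practical considerations and anticipated attrition based on our prior studies", and concludes: "The resulting 30 participants per group will be sufficient for estimating preliminary efficacy". No alpha, power, SD, effect size or interval width is given.

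SAP A.3 sets out the Aim 2 analysis: "Effect sizes will be estimated by fitting ANCOVA models with treatment group as the explanatory variable", with omega-squared as the effect measure and analysis by intention to treat.

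The Protocol's Amendment Form (A016) gives the study status as "Closed to Enrollment", with interventions still running. Under the rationale for the change it says: "Previous enrollment numbers are not significant for complete data analysis". The change is to recruit current control participants into SystemCHANGE. The amended procedures in section B (Lay Summary Research Design) make this voluntary, with a further 12 weeks of electronic monitoring. The rationale concedes that this is not a proper crossover, yet presents it as added enrolment in the SystemCHANGE arm that will help secure later funding.

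The SAP does not mention A016.

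**The concern.** A016 is the live amendment, not a log of superseded text, so the two documents conflict as they stand. The SAP's only statement on size says the number is enough. The amendment says recruitment has ended and the numbers reached fall short of what a complete analysis needs.

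Two things are at stake. First, the Aim 2 effect size is meant to help justify a larger trial. A reader who takes 30 per group from the SAP would credit it with more precision than a smaller randomised comparison has. Second, because the amendment speaks of switched controls as enrolment, they could be added to the SystemCHANGE total so that the arm appears to reach its size. The SAP has no rule to prevent this. Its ANCOVA has one treatment-group term and does not say how to treat a person who has been in both groups.

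**Working it through.** **1. The plan's own figure.** Inputs from SAP A.2: 66 enrolled, 60 retained, 60/2 = 30 per group. The implied attrition is 1 − 60/66 = 9.1%. Inflating 60 by 1/(1 − d) gives 66 at d = 8% or 9% and 67 at 10%; 60 × 1.10 is exactly 66. The step from 60 to 66 is sound. The 30 per group has no calculation behind it to reproduce.

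**2. What the closure implies.** Set side by side, the SAP says "we will enroll 66 individuals, to retain 60" and the amendment says "Previous enrollment numbers are not significant for complete data analysis". Reading 'not significant' as 'not sufficient' is the natural sense, since the amendment goes on to add SystemCHANGE exposures. The achieved number is not given. The total of 150 under Participant Information does not settle it: section B has people join a two-month monitoring phase and be randomised only if adherence is below 0.85, and the form does not say whether 150 counts people screened or randomised.

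**3. What switching adds.** If n are randomised to each arm and m controls later take SystemCHANGE, the SystemCHANGE exposures become n + m, but the randomised comparison stays n versus n. No control is added, and the m extra records come from people already in the comparison.

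**4. Precision over a range of sizes.** The sizes below 30 are assumptions. The half-width for a between-arm mean difference, in SD units, with equal arms and no covariate, is t(0.975, 2n − 2) × √(2/n). The standard error relative to 30 per arm is √(30/n).

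| n per arm | 95% half-width (SD) | Standard error relative to 30 per arm |
|---|---|---|
| 30 | 0.52 | 1.00 |
| 25 | 0.57 | 1.10 |
| 20 | 0.64 | 1.22 |
| 15 | 0.75 | 1.41 |
| 10 | 0.94 | 1.73 |

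**5. Effect on the planned measure.** Assume a true difference of 0.5 SD. The population omega-squared is then (0.5²/4)/(1 + 0.5²/4) = 0.059. In 50,000 simulated trials per size, the central 95% of estimates ran from −0.02 to 0.21 at 30 per arm and from −0.03 to 0.28 at 15. The chance of an estimate at or below zero rose from 17% to 34%.

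**6. Why pooling does not rescue precision.** Suppose 15 were randomised to each arm and all 15 controls switched. Comparing the 30 SystemCHANGE records with the 15 control records is not a comparison of independent groups. With within-person correlation ρ, the variance of the difference is σ²(1.5 − ρ)/15. The nominal half-width (1.96 × standard error) is 0.62 SD at ρ = 0 and 0.51 SD at an assumed ρ = 0.5. The second figure looks like 30 per arm, but it describes a partly before-and-after contrast, not the randomised one.

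**The case against.** The strongest reply is that A.2 is prospective. Missing a target does not make the target wrong, and achieved numbers normally go in the report. This stands to the extent that the planned 66, 60 and 30 should remain visible; overwriting them would hide the miss. It does not answer the sufficiency claim, which is conditional on 30 per group, nor the need to settle before analysis how second-exposure data are treated. Numbers retained may not exist yet, since interventions continue and follow-up runs to 12 weeks.

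Safeguards exist. The SAP says efficacy estimates will not be the only basis for sizing the larger study, promises enrolment and completion proportions, specifies intention to treat, and acknowledges a small sample. The amendment is open about not being a crossover. These limit the harm but do not state the size actually available or exclude the second exposures.

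Three stronger readings are tempting and not supported. A reader might infer that the trial misses a stated precision; the SAP states none. A reader might treat the shortfall as documented; it is inferred from the closure and the rationale, with no number given. A reader might conclude that the sponsor intends to count switched controls toward 30 per group or put them in the ANCOVA; no passage says so, and the defect is that nothing excludes it.

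It is also fair that the half-widths above are unadjusted. A baseline covariate in the ANCOVA would narrow them all, but the documents give no correlation from which to say by how much.

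**Conclusion.** The point holds as a conflict between the SAP's sufficiency claim and the current amendment. That the SAP has not been updated, and that switching cannot restore 30 versus 30, can be confirmed from the documents. The size of the shortfall cannot. If 20 per arm were retained, the half-width would be 0.64 SD against 0.52 at the planned size; at 15 per arm it would be 0.75 SD, with a standard error 41% larger. These figures assume equal arms and no gain from covariates. The SAP should be corrected before the Aim 2 analysis, but its planning arithmetic contains no error.

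**What to change.** In SAP A.2:

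- Keep the planned target, and beside it give the numbers randomised per arm at closure. Add the numbers retained per arm when follow-up ends.
- Withdraw the claim of sufficiency if 30 per group is not reached.
- Give the 95% confidence interval half-width for the between-arm adherence difference at the achieved size.

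In A.2 and A.3, state that data from control participants' later SystemCHANGE exposure under A016 do not count toward the per-group size and do not enter the randomised Aim 2 ANCOVA. Summarise those data separately as a non-randomised second exposure.

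The cost is wording only. The downside for the sponsor is that the stated size and expected precision will look less favourable. No further enrolment is requested.

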**B-Lay Summary Research Design**

**Describe the purpose of this study in lay terms, including research question(s) and hypothesis.**

The purpose of this-group, randomized, controlled trial is to evaluate the refined SystemCHANGE™ against attention control patient education in CKD patients taking RAAS medications. Patients will be recruited from two sources: 1) the largest and most comprehensive health care system in the state and 2) one of the largest essential health care systems in the country. Data are collected at baseline, 8 weeks(immediately post-intervention)and 12 weeks. Specific aims are to: Aim 1. Estimate acceptability, outcome expectancy and credibility of the refined SystemCHANGE™ Intervention and for the attention control at 8 and 12 weeks after baseline. Aim 2. Estimate preliminary efficacy of SystemCHANGE™ Intervention versus attention control on medication adherence (primary outcome) and personal systems behavior (mechanism of action) at 8 and 12 weeks among people with CKD taking a once-daily RAAS inhibiting medication. The immediate impact of this study will be data to inform the design of a future, fully powered, efficacy trial. If findings are as expected, we will proceed to an R01 application. If findings are not as expected (e.g., negative), we will work to improve the SystemCHANGE™ intervention or move to a different intervention in future trials. The long-term impact of this line of research will be additional empirical evidence for novel medication adherence interventions in this population to inform future evidence-based guidelines, position statements, and practice recommendations.

**List and describe all research interactions and/or interventions, including the frequency and duration of procedures, and length of participation for individual subjects.**

WHAT WILL HAPPEN DURING THE STUDY? This study has 3 phases- the screening phase, the intervention phase, and the maintenance phase. Before being invited to participate in this study, you will be asked questions from the 6-item cognitive screening survey to make sure you qualify for the study.

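### The Aim 2 ANCOVA names neither screening adherence nor the stratum built from it as a covariate; naming the score is a free but minor gain

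*SAP*

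**What the plan says.** SAP A.3 (Analytic Plan) describes the Aim 2 model in one sentence: "Effect sizes will be estimated by fitting ANCOVA models with treatment group as the explanatory variable and outcomes: 1) adherence and 2) personal systems behavior". The next gives the metric: "Effects sizes will be estimated with" omega-squared. A covariate appears only in the supplementary analyses, which look at "the adjustment for levels of the covariate (e.g. male and female for sex") through interaction terms and separate estimates. No covariate list for the main model is given in the SAP or the protocol.

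SAP A.1 states "Randomization will be stratified by" moderate (.70-.84) and low (<.70) adherence, and describes the study as "using repeated measures in adults with CKD and poor adherence to prescribed RAAS inhibitor medication".

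The protocol's description of the screening phase and its inclusion criterion 4 require a monitored adherence score below .85 before random assignment. Every randomised participant therefore has a pre-randomisation measure of the primary outcome. Aim 2 in the protocol concerns "medication adherence (primary outcome) and personal systems behavior (mechanism of action) at 8 and 12 weeks".

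**The concern.** The plan collects the natural covariate for its primary outcome and stratifies on it, but does not say that it enters the model. Two analysts could fit different models and both claim to follow A.3.

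If neither the score nor the stratum is fitted, two separate things follow.

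- Stratification makes the arms more alike than chance would, and a treatment-only model does not credit this. Its standard error is too large. Adding either term repairs this.
- Differences in adherence within a stratum stay in the error term. Only the continuous score removes them.

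This matters because a purpose of the trial is "to calculate preliminary effect size estimates (Aim 2") from about 30 participants per arm.

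**Working it through.** **The plan's own figure.** SAP A.2 enrols 66 to retain 60. The implied attrition is 6/66 = 9.1%, and 60/(1 - 6/66) = 66, so the figures agree. Because the rate is back-calculated from the same two numbers, this checks consistency only. The sample size rests on a pilot-study rule of 30 per group, so the choice of model does not affect it.

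**Inputs.** From the documents: N = 60 analysed, 30 per arm; two strata cut at .70; entry below .85. Assumed:

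- r between screening and follow-up adherence among those randomised, shown as a range;
- a normal score and a linear relation;
- 30-70% of participants in the low stratum;
- near-exact balance of arms within each stratum (the SAP does not describe blocks).

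Outcome SD is set to 1.

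**Plausible r.** Restriction to scores below .85 probably lowers r. With r = 0.5 among all screened, a normal score and half of those screened below .85 (SD ratio u = 0.603), r' = 0.5 × 0.603/√(0.75 + 0.25 × 0.603²) = 0.33. Bounded (Beta) shapes give 0.42-0.50. So 0.2 to 0.5 is the range to read first, and 0.7 is an upper limit.

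**Formulas.** B is the share of baseline variance lying between strata: 0.637 if half are in the low stratum, 0.576 if 30% or 70% are.

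- Treatment only, true SD = √[(4/60)(1 - B r²)].
- Treatment only, standard-error excess ≈ 1/√(1 - B r²) - 1.
- Treatment plus score, SD ≈ √[(4/60)(1 - r²)(1 + (1 - B)/59)].

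Example at r = 0.5, B = 0.637: the true SD is √(0.06667 × 0.841) = 0.237, and the excess is 1/√0.841 - 1 = 9.1%. With the score, the SD is √(0.06667 × 0.75 × 1.006) = 0.224, a fall of 5.3%.

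| r | True SD, treatment only | SE excess, B = 0.637 | SE excess, B = 0.576 | SD with score | Change in true SD (B = 0.637; 0.576) |
|---|---|---|---|---|---|
| 0 | 0.258 | 0% | 0% | 0.259 | +0.3%; +0.4% |
| 0.2 | 0.255 | 1.3% | 1.2% | 0.254 | -0.4%; -0.5% |
| 0.33 | 0.249 | 3.7% | 3.3% | 0.244 | -1.8%; -2.1% |
| 0.5 | 0.237 | 9.1% | 8.1% | 0.224 | -5.3%; -6.1% |
| 0.7 | 0.214 | 20.6% | 18.0% | 0.185 | -13.6%; -15.4% |

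SDs are for B = 0.637. Simulation agrees to within 0.001. At r = 0.5 the treatment-only model reports a mean standard error of 0.258 against a true SD of 0.237. With the score it reports 0.223 against 0.224.

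**Bounded baseline.** Sixteen Beta shapes cut at .70 and .85 give B = 0.51-0.67 and a standard-error excess of 1.0-1.4%, 2.9-3.9% and 7.1-9.7% at r = 0.2, 0.33 and 0.5.

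**Test size.** In a separate simulation of 20,000 runs, a nominal 5% test without either term rejects in 4.2%, 3.4% and 1.8% of null trials at r = 0.3, 0.5 and 0.7. With the score alone it rejects in 4.9%, 5.0% and 4.9%.

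**Score alone or score plus stratum.** Change in true SD against treatment only, at r = 0.33 and 0.5:

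| Per arm | Score alone | Score plus stratum |
|---|---|---|
| 20 | -1.8%, -5.2% | -0.9%, -4.3% |
| 12 | -1.3%, -4.9% | +0.3%, -3.1% |

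The stratum adds nothing once the score is in, and it costs precision in small samples.

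**Omega-squared.** For a true 0.5 SD difference, total omega-squared is 0.0625/1.0625 = 0.059 whatever r is. The partial version with the score is 0.0625/(0.0625 + 1 - r²) = 0.061, 0.066 and 0.077 at r = 0.2, 0.33 and 0.5. One trial's value has a sampling SD of about 0.05-0.07.

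**The case against.** The strongest reply is that a treatment-only model is not what the plan says. ANCOVA has a covariate by definition, A.3 refers to one, and the design has a baseline assessment, so adjustment for baseline adherence is a natural reading. This stands. A reader might infer that the plan omits baseline adjustment; the documents support only that the covariates are not identified. The figures above describe what happens if neither term is fitted.

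The second reply is that little harm follows. The standard-error fault is conservative, and A.3 promises omega-squared with no standard error, test or interval. At r of 0.2 to 0.33 the true SD falls by about 2% or less. SAP A.2 also says that "efficacy estimates themselves will not solely be used to determine the sample size for the larger study". All of this stands and sets the weight of the point.

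Third, r is not in the documents, and the model assumes a linear relation with constant variance for an outcome that is a bounded score. The bounded check varies the baseline shape only. This also stands, which is why a range is shown.

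What survives is narrow: the score is held for everyone, it underlies the randomisation, and no sentence commits the analyst to using it.

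**Conclusion.** The point holds as a minor, free improvement. A.3 should name its covariate, and screening adherence is the obvious one for the adherence outcome. Without it or the stratum, any interval would be about 1%, 3-4% or 8-9% too wide at r = 0.2, 0.33 or 0.5, and the score would lower the true SD by about 0%, 2% or 5-6%. These sizes rest on an assumed r, a linear model, balance within strata and 30 per arm.

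Three stronger readings are not supported:

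- **Bias.** Allocation is randomised, so the treatment difference is unbiased with or without the covariate.
- **The stratum must be in the model.** The score alone already gives a correct standard error.
- **The effect size is unusable because omega-squared is not labelled partial or total.** At low r the two versions differ by far less than the sampling variation of one trial. The label and the time point are reporting details and do not carry this point.

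**What to change.** In A.3, before outcomes are compared by arm:

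- State the adherence model as treatment plus continuous screening adherence. Adding the stratum is optional and is better left out if few participants are analysed, which is a realistic case because the protocol's amendment rationale reports insufficient enrolment.
- For personal systems behavior, use treatment plus its own baseline score if that is collected before the intervention, and otherwise treatment plus stratum. The protocol says that data are collected at baseline, but its description of procedures does not say when this measure is taken.
- When reporting, label omega-squared as partial or total and give the time point (8 or 12 weeks).

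The sex analyses can stay supplementary as planned.

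The cost is two or three sentences, no new data and one degree of freedom (57 instead of 58 at 30 per arm). If r were zero, the SD would rise by about 0.3% at 30 per arm, 0.5% at 20 and 0.9% at 12.
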